ENDPOINTS	
Primary efficacy endpoint(s) Not applicable.
 
Secondary efficacy endpoints Not applicable.
 
Main safety and tolerability endpoints The main safety and tolerability endpoints will be analyzed over the Period 1, Period 2, and Period 3 combined.
 
• Discontinuations due to prostacyclin-associated adverse events (AEs).• AEs and serious AEs (SAEs).• Prostacyclin-associated AEs.• AEs related to injection site reactions.• PAH-related AEs. 
Other endpoints Other endpoints are described in Section 6.2.3.

PHARMACOKINETIC ENDPOINTS	
• The AUC during a dose interval at steady state ($AUC_{\tau, ss}$) of selexipag and its active metabolite, ACT-333679, at steady state after Uptravi (oral selexipag) in Period 1 and after i.v. selexipag administration in Period 2.• The maximum plasma concentration at steady state ($C_{max, ss}$) of selexipag and its active metabolite, ACT-333679 after Uptravi (oral selexipag) in Period 1 and i.v. selexipag administration in Period 2.• The time to reach maximum plasma concentration at

Confidential

	
steady-state ($t_{max, ss}$) of selexipag and its active metabolite, ACT-333679 after Uptravi (oral selexipag) in Period 1 and i.v. selexipag administration in Period 2.
 
• Trough plasma concentration at steady state ($C_{trough, ss}$) of selexipag and its active metabolite, ACT-333679 after Uptravi (oral selexipag) in Period 1 and i.v. selexipag administration in Period 2.
ASSESSMENTS	Refer to the schedule of assessments in Table 2 .

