6.2.2 Main safety and tolerability endpoints

The main safety and tolerability endpoints will be analyzed over Period 1, Period 2, and Period 3 and follow-up period combined.

- Discontinuations due to prostacyclin-associated AEs.
- AEs and SAEs.
- Prostacyclin-associated AEs.
- AEs related to injection site reactions.
- PAH-related AEs.

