2.3 Analysis periods

The study comprises five analysis periods:

Screening period: This period starts with the signing of the Informed Consent Form and ends with the first day of Period 1 (Visit 2 Day 1).

Period 1 (Uptravi, pre-treatment period, in-hospital): This period starts with intake of the morning dose of Uptravi at Visit 2 Day 1, and ends the following day before initiation of the first infusion of i.v. selexipag.

Period 2 (i.v. selexipag, treatment period, in-hospital): This period starts in the morning of Visit 2 on Day 2 with the start of the first infusion of i.v. selexipag, and ends after approximately 36 hours in the evening of Visit 2 on Day 3 with the resuming of administration of Uptravi at the evening dose.

Period 3 (Uptravi, post-treatment period): This period starts in the evening of Visit 2 Day 3 with the first dose of resumed oral administration of Uptravi, and ends 7 to 11 days later at Visit 3.

Safety follow-up period: This period starts at the end of Visit 3 and ends 30 to 37 days after the last administration of i.v. selexipag with the End-of-Study (EOS) telephone call (Visit 4).

[figure not shown]
A summary of analysis periods is presented in [Table 2](#):

Table 2 Summary of analysis periods

Period	Start	Stop
Screening period	Date/time of first Informed consent form signature	Prior to morning dose of Uptravi at Visit 2 Day 1
Period 1: Uptravi, pre-treatment period	Date/Time of Uptravi morning dose intake at Visit 2 Day 1	Prior to start of first infusion of i.v. selexipag at Visit 2 Day 2
Period 2: i.v. selexipag, treatment period	Start date/time of first infusion of i.v. selexipag at Visit 2 Day 2	Prior to evening dose of Uptravi at Visit 2 Day 3
Period 3: Uptravi, post-treatment period	Date/time of Uptravi evening dose intake at Visit 2 Day 3	Visit 3
Safety follow-up period	After end of Visit 3	End of Study

The study design and flow is shown in Figure 1 below. For details, refer to section 3 and section 7 of the AC-065A309 study protocol [D-17.055].

Figure 1 Study design and flow

* 12-hour PK profile after the morning dose.

** For convenience, hospitalization may be extended to the night before Day 1 and to the night of Day 3.

D = day; EOS = End-of-Study; IV1–IV3 = dose of i.v. selexipag; PK = pharmacokinetic; V = visit.

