7 SAFETY VARIABLES

7.1 Overview of safety analyses including subgroup analyses

7.1.1 Overview of safety and tolerability endpoints

Safety endpoints in this study comprise the incidence of AEs and serious AEs (SAEs), discontinuations due to AEs, change and newly occurring abnormalities in vital signs, ECG and clinical laboratory values, as well as change in WHO FC and body weight.

The analysis of safety endpoints in different analysis periods [see [Table 2](#)] is summarized in [Table 7](#) below.

Table 7 Overview of safety and tolerability endpoints and populations in planned analysis periods

Endpoint	SCR (Scr)	1 (S)	2 (ivS)	3&FU (ivS)	1&2 (S)	2&3&FU (ivS)	1&2&3&FU (S, ivS)
Main safety and tolerability endpoints							
AEs and SAEs	✓	✓	✓	✓	✓	✓	✓
Prostacyclin-associated AEs ¹ leading to discontinuation of study drug			✓				
Prostacyclin-associated AEs ¹		✓	✓	✓	✓	✓	✓
Injection site reaction AEs ¹			✓				
PAH related AEs ¹		✓	✓	✓	✓	✓	✓
Other safety and tolerability endpoints							
AEs leading to discontinuation of study drug				✓			
AEs related to study drug as judged by the investigator			✓	✓		✓	✓
Deaths during study							✓
ECG abnormalities, QT prolongation		✓	✓	✓	✓	✓	✓
Marked laboratory abnormalities		✓	✓	✓		✓	✓
Marked blood pressure abnormalities		✓	✓	✓		✓	✓
Change from baseline in WHO functional class ²		✓	✓	✓	✓	✓	✓

Periods connected by an ampersand will be analyzed combined.

All analyses will be run on the S, if S and ivS are identical.

¹ As defined by MedDRA search terms ² By visit analyses

(S) = Safety analysis Set, (ivS) = i.v. Safety analysis set, (Scr) = Screened subject set; AE = adverse event; ECG = electrocardiograph; FU = Safety Follow Up; MedDRA = Medical Dictionary for Regulatory Activities; PAH = pulmonary arterial hypertension; SAE = serious adverse event; SCR = Screening period, WHO = World Health Organization.

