7.2 Adverse events

7.2.1 Variables

The original verbatim terms used by investigators to identify AEs in the eCRF will be mapped to PTs using the MedDRA dictionary using the latest version at data cutoff. The AE PTs will be then grouped by MedDRA PTs into frequency tables according to primary SOC.

7.2.1.1 *Treatment-emergent adverse events*

The analysis of AEs in Period 2, Period 3 and safety follow-up period is considered analysis of treatment-emergent events, as the i.v. formulation is the investigational treatment.

7.2.1.2 *Adverse events related to study treatment*

An AE will be considered related to the study treatment if the investigator answered 'yes' to the question 'Causal relationship to i.v. selexipag' or if it is missing.

7.2.1.3 *Serious adverse events*

An AE will be considered serious if the investigator answered 'Yes' to the question 'Serious?' or if information is missing.

7.2.1.4 *Adverse events leading to discontinuation of study treatment*

An AE is considered as leading to discontinuation of study treatment if the investigator ticked 'Drug withdrawn' on the question 'Action taken with study treatment'.

7.2.1.5 *Injection site reactions*

Injection site reactions will be collected on a separate eCRF page. Clinically significant injection site reactions will be reported as an AE.

7.2.1.6 *Prostacyclin-associated AEs*

Prostacyclin-associated AEs are AEs associated with the pharmacological action of selexipag that have been observed frequently, in particular during the phase of individualized dose titration. According to selexipag Investigator's Brochure (IB) reference safety information, these PTs include headache, diarrhea, nausea, vomiting, jaw pain, myalgia, pain in the extremity, flushing, and arthralgia.

7.2.1.7 *AEs of special interest based on the Utravi Risk Management Plan*

For completeness, AEs will be analyzed according to the Utravi Risk Management Plan (RMP) important identified or potential risks, using searches of MedDRA PTs provided by Global Drug Safety at the time of database closure. In accordance with the RMP, the following categories will be analyzed:

- Hypotension
- Anemia, decrease in hemoglobin concentration

- Hyperthyroidism
- Major adverse cardiovascular events
- Acute renal failure
- Bleeding events
- Light-dependent non-melanoma skin tumors
- Ophthalmological effects associated to retinal vascular system

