7.2.2 Analysis

The start date/time of the AE record from the CRF will be used to assign the AE to a study period.

Summary tables will be prepared as described in [Table 8](#) for the periods mentioned in [Table 7](#), except for the screening period.

Summary tables by SOC and PT will display the number and percentages of subjects with at least one AE in the respective primary SOC and at least one AE at the PT level. Summaries will be sorted by descending total frequency of SOCs and PTs and alphabetically in case of ties.

Summary tables by PT will display the number and percentages of subjects with at least one AE in the respective PT. Summaries will be sorted by descending total frequency of PTs and alphabetically in case of ties.

AEs occurring during the Screening period, i.e., prior to first dose of Uptravi on Visit 2 Day 1, will be listed.

Due to the small number of subjects, conservative 95% Clopper-Pearson CIs for the proportions will be computed using exact methods.

All AEs occurring during the study from date of informed consent signature to EOS will be listed.

For any injection site reaction (irrespective of clinical significance), the worst grade, criteria of the injection site reaction, as well as its clinical significance will be summarized. Any AEs associated with clinically significant injection site reactions will be summarized by PT and by maximum intensity in the AE table.

Table 8 Overview of adverse event analyses

Category	Approach
All AEs	
- N (%) of subjects having at least one AE by primary SOC and PT- N (%) of subjects having at least one AE by PT- N (%) of subjects having at least one AE by PT and maximum intensity- Listing
SAEs	
- N (%) of subjects having at least one SAE by PT- Listing
Injection site reaction AEs	
- N(%), grade and diagnosis criteria of injection site reactions- N (%) of subjects having at least one clinically significant injection site reaction by PT and maximum intensity- Listing of PTs and specific details
Prostacyclin-associated AEs	
- N (%) of subjects having at least one prostacyclin associated AE by PT- N % of subjects having at least one prostacyclin associated SAE by PT- N % of subjects having least one prostacyclin associated AE leading to discontinuation of study drug by PT- Listing

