<Preferred term 8>	xxx (xx.x)	xx.x, xx.x	xxx (xx.x)	xx.x, xx.x	xxx (xx.x)	xx.x, xx.x
...						

CI = Confidence interval

Preferred Terms are based on MedDRA version <xx.x>.

Output: <Output name>, Produced by DATAMAP on ddMMyyyy hh:mm (CET),

SDTM Date: ddMMyyyy

Program: /<folder>/<program_name>.sas

Page x of y

Programming note: Sort by descending frequency and then alphabetically in the PTs in total. Use the following labels:

Analysis Period	Label in summary table
1	Period 1: Uptravi, pre-treatment period
2	Period 2: i.v. selexipag, treatment period
3&FU	Period 3: Uptravi, post-treatment period including safety follow-up period
1&2	Period 1 & 2: Uptravi, pre-treatment period and i.v. selexipag treatment period combined
2&3&FU	Period 2 & 3: i.v. selexipag, treatment period and Uptravi, post-treatment period including safety follow-up period combined
1&2&3&FU	Period 1 & 2 & 3: All post-baseline periods including safety follow-up period

T_AE_PT_INT

ACT-293987

Protocol: AC-065A309

Incidence of adverse events by preferred term and maximum intensity

Analysis Set: <Analysis set>

Preferred Term Intensity	Uptravi b.i.d. dose		
	200-1000 ug N=xxx n (%)	1200-1600 ug N=xxx n (%)	Total N=xxx n (%)
Subjects with at least one AE			
Mild	xxx (xx.x)	xxx (xx.x)	xxx (xx.x)
Moderate	xxx (xx.x)	xxx (xx.x)	xxx (xx.x)
Severe	xxx (xx.x)	xxx (xx.x)	xxx (xx.x)
Missing	xxx (xx.x)	xxx (xx.x)	xxx (xx.x)
<Preferred term 1>			
Mild	xxx (xx.x)	xxx (xx.x)	xxx (xx.x)
Moderate	xxx (xx.x)	xxx (xx.x)	xxx (xx.x)
Severe	xxx (xx.x)	xxx (xx.x)	xxx (xx.x)
Missing	xxx (xx.x)	xxx (xx.x)	xxx (xx.x)
<Preferred term 2>			
Mild	xxx (xx.x)	xxx (xx.x)	xxx (xx.x)
Moderate	xxx (xx.x)	xxx (xx.x)	xxx (xx.x)
Severe	xxx (xx.x)	xxx (xx.x)	xxx (xx.x)
Missing	xxx (xx.x)	xxx (xx.x)	xxx (xx.x)

The maximum intensity of the AE is shown.

All post-baseline AEs are shown (Period 1 & 2 & 3 including safety follow-up)

Preferred Terms are based on MedDRA version <xx.x>.

Output: <Output name>, Produced by DATAMAP on ddMMMyyyy hh:mm (CET),

SDTM Date: ddMMMyyyy

Program: /<folder>/<program_name>.sas

Page x of y

Programming note: Sort by descending frequency and then alphabetically in the PTs. Show missing category only if it occurred in the data.

T_AEINJ

ACT-293987

Protocol: AC-065A309

Grade and diagnosis criteria of injection site reactions

Analysis Set: i.v. Safety Analysis Set

	Uptravi b.i.d. dose 200-1000 ug N=xxx n (%)	1200-1600 ug N=xxx n (%)	Total N=xxx n (%)

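### SAP Table 7 gives injection site reaction AEs a single-period window that conflicts with protocol 6.2.2 and with the SAP's own output shell

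*SAP*

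**What the plan says.** Protocol 6.2.2 lists "AEs related to injection site reactions" as a main endpoint and sets one window for all endpoints in that list: "The main safety and tolerability endpoints will be analyzed over Period 1, Period 2, and Period 3 and follow-up period combined". The protocol synopsis is slightly shorter: "The main safety and tolerability endpoints will be analyzed over the Period 1, Period 2, and Period 3 combined". It does not name follow-up, but it does include Period 3.

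SAP 7.1.1, Table 7, keeps "Injection site reaction AEs" under the main endpoints. The row has one tick, which in the text available falls in the Period 2 column. The cell for Periods 1, 2, 3 and follow-up combined is empty. SAP 7.2.2 says that the AE summary tables are produced for the periods in Table 7, screening excepted, and adds: "The start date/time of the AE record from the CRF will be used to assign the AE to a study period". SAP 2.3 ends Period 2 at this point: "Prior to evening dose of Uptravi at Visit 2 Day 3".

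The SAP's output specification reads differently. Section 12.7.5 lists AE_INJ_INT, a key deliverable, with no period in its title, and assigns it the shell T_AE_PT_INT. The footnote of that shell in Appendix E states: "All post-baseline AEs are shown (Period 1 & 2 & 3 including safety follow-up". SAP 11.1 records no change to the analyses planned in the protocol, and 11.3 does not mention this endpoint.

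**The concern.** One main endpoint has two pre-specified windows. A programmer who works from 7.2.2 and Table 7 would count reactions with onset in Period 2 only. One who works from the shell would count all post-baseline onsets. The two could report different numbers in a key deliverable, and the choice could be made after the data are seen. If the narrower window were used, it would be an undeclared departure from the protocol.

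The endpoint carries weight in this trial. Protocol 1.4 expects the risks of participation to be limited to those of i.v. administration and of the invasive study procedures. Protocol 1.2.4 says that earlier i.v. experience was with a different formulation, in 18 healthy men. Local tolerability of the present formulation is thus one of the few risks that this trial is placed to describe.

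**Working it through.** **Step 1. The statements side by side**

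| Source | Window for injection site reaction AEs |
|---|---|
| Protocol 6.2.2 | Periods 1, 2, 3 and follow-up combined |
| Protocol synopsis | Periods 1, 2, 3 combined; follow-up not named |
| SAP Table 7 with 7.2.2 | One tick, printed under Period 2; AEs placed by onset |
| SAP 12.7.5, AE_INJ_INT, shell T_AE_PT_INT | All post-baseline periods including follow-up |
| SAP 12.7.5, AE_INJDET, shell T_AEINJ | All injection site reactions; no period limit stated |
| SAP 12.9, listing AE_INJDET | All injection site reactions; no period limit stated |
| SAP 11.1 | No change from the protocol declared |

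Only Table 7, made operative by 7.2.2, is narrower than the protocol. No sentence in the SAP ranks Table 7 above the shells, or the shells above Table 7.

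**Step 2. Where the Period 2 cut falls**

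Inputs: the infusion scheme (protocol 5.1.4), the period boundaries (SAP 2.3) and the nominal dosing times (protocol Table 3: third infusion 24 h after the first, evening Uptravi 12 h after the start of the third).

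- Infusion length: 5 mL at 20 mL/h plus 45 mL at 37.5 mL/h = 15 + 72 = 87 min = 1.45 h, which reproduces the protocol's figure.
- Period 2 length: 24 + 12 = 36 h.
- Time from the end of each infusion to the end of Period 2: first, 36 − 1.45 = 34.55 h; second, 24 − 1.45 = 22.55 h; third, 12 − 1.45 = 10.55 h.

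**Step 3. Comparison with the treatment-emergent window**

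SAP 7.2.1.1 states: "The analysis of AEs in Period 2, Period 3 and safety follow-up period is considered analysis of treatment-emergent events". Protocol 9.1.1 runs that window to 30 days after the last infusion ends.

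- Length: 24 + 1.45 + 30 × 24 = 745.45 h.
- Share covered by Period 2: 36 / 745.45 = 4.8%.

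This is a share of calendar time. It says nothing about the share of reactions, because all three infusions lie inside Period 2.

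**Step 4. What a late reaction would still appear in**

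A reaction with onset after Period 2 that is reported as an AE falls in the all-AE tables, which Table 7 ticks for 3&FU, 2&3&FU and 1&2&3&FU. It also appears in the listing of all injection site reactions. What is at risk is its place in the summary of this endpoint.

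**The case against.** The strongest reply is that nothing is lost. Every injection site output in the SAP is written without a Period 2 limit, and the footnote of the AE_INJ_INT shell names the full window. Table 7 is only titled an overview. Its single-tick AE rows also match the outputs whose titles do not mention periods (AE_INJ_INT, AE_PCDC_PT, AE_DC_PT), so one tick might mean one table not split by period. The column of the tick is open to doubt as well: in the same table, discontinuation for any AE is ticked under 3&FU, although study drug is given only in Period 2.

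Much of this stands. A reader might infer from Table 7 that delayed reactions drop out of the analysis. The documents do not support that as a flat statement, because it follows only if Table 7 prevails over the shell. A reader might also think that this is the only main AE endpoint with a restricted window. It is not: the row for prostacyclin-associated AEs leading to discontinuation also has one tick.

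The reply does not remove the conflict. SAP 7.2.2 expressly takes the periods from Table 7. T_AE_PT_INT is a shared shell that carries the title of the all-AE intensity table, so its footnote may not have been written with this endpoint in mind. A single tick in any column other than 1&2&3&FU would still leave out the window that protocol 6.2.2 requires.

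**Conclusion.** The point holds as an inconsistency within the SAP and an undeclared mismatch between Table 7 and protocol 6.2.2. If Table 7 is followed, reactions with onset after the Day 3 evening Uptravi dose, nominally 10.55 h after the third infusion ends, are left out of this endpoint's summary. If the shell is followed, they are counted.

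A reader might take the 4.8% in the working as the fraction of reactions captured. It is not, and the documents give no rate or timing of late reactions from which such a fraction could be found. A reaction that starts in Period 2 but is noticed later still belongs to Period 2, because assignment is by onset.

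The conclusion assumes nominal dosing times and that the single tick was printed as read; its exact column may have been affected by extraction from PDF. No sample size, precision statement or error rate is touched. The correction is worth making because the endpoint is a main one and the cost is close to nil.

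**What to change.** In SAP Table 7, tick 1&2&3&FU for the injection site reaction row and keep Period 2 as a by-period display. Protocol 6.2.2 requires only the combined window, and the per-period list in protocol 6.2.3 does not name this endpoint, so ticks for 3&FU and 2&3&FU are optional. That column of Table 7 already allows for the i.v. Safety Set, which is the set AE_INJ_INT uses.

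State the same window in the titles of AE_INJ_INT and AE_INJDET in SAP 12.7.5, so that Table 7, the outputs and the protocol agree. If a Period 2 restriction was intended, declare and justify it in SAP 11.1 and correct the shell footnote for this table.

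Either route costs a table entry and two titles or a short paragraph. It needs no new data collection and no new analysis method.

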6.2.3 Other safety and tolerability endpoints

The other safety and tolerability endpoints will be analyzed:

- For each study period separately: Period 1; Period 2; Period 3 and follow-up period combined.
- For Period 1 and Period 2 combined.
- For Period 2 and Period 3 combined.

The following endpoints will be analyzed:

- Discontinuations due to prostacyclin-associated AEs.
- Discontinuations due to any AEs.
- AEs and SAEs.
- Prostacyclin-associated AEs.
- PAH-related AEs.

- Change from baseline in vital signs (SBP, diastolic blood pressure [DBP], and pulse rate) and body weight.
- ECG abnormalities.
- Marked laboratory abnormalities (MLAs).
- Change from baseline in WHO FC.

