10.2 Analysis periods and visit windows

10.2.1 Study treatment start and end date

The date and time of the first infusion of i.v. selexipag will be considered study treatment start date/time. The end date and time of the last infusion of i.v. selexipag will be considered study treatment end date/time.

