10.5 Handling of missing/incomplete date and time fields

Missing parts for specific dates/times will be changed into acceptable non-missing values as described in the table below.

Type of date/time	Imputation method when date/time is incomplete	Imputation method when date/time is missing
Start Date/Time of Adverse Event	If the end date of the AE is not before the start of study treatment, and if the study treatment start falls in the range of possible dates, the study treatment start date is used. In all the other cases, the lower limit (i.e., first day of the month, 00:00h) is used.	Date & time of first i.v. selexipag
End Date/Time of Adverse Event	Use the upper limit of the range of possible dates given the nonmissing date/time parts, i.e., last day of the month or last day of the year, 23:59h	No approximation, the AE is considered ongoing at end of study

Start Date of Medication	If the date of the Screening visit is within the range of possible dates, use the Screening visit date. Otherwise, use first day of the month and/or first day of the year.	Date of Screening visit
End Date of Medication	Use the upper limit of the range of possible dates given the nonmissing date/time parts, i.e., last day of the month or last day of the year	No approximation, the medication is considered ongoing at the end of study
Date of initial diagnosis of PAH	Day missing: 15th of the month Day and month missing: 30th of June If the resulting date is later than the date of screening visit date and the lower limit is not later than the screening visit date, then the date is substituted with the date of screening visit.	No replacement
PK sample Date/Time	If the scheduled time is within the possible range given the nonmissing date/time parts, use the scheduled date/time. Otherwise, the sample date/time cannot be imputed.	No replacement

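### SAP Table 7 plans the all-cause summary of AEs leading to i.v. discontinuation for one period only, read as Period 3 with follow-up, and does not cover the periods in protocol 6.2.3

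*SAP*

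**What the plan says.** Protocol 6.2.3 lists "Discontinuations due to any AEs" among the other safety endpoints. It asks for these endpoints in Period 1, Period 2, and Period 3 with follow-up separately, and in Periods 1 and 2 and Periods 2 and 3 combined. Protocol 10.3.4 adds a summary across all periods and tabulation on both the Safety Set and the i.v. Safety Set, with an exact 95% interval for the proportion.

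SAP Table 7 (section 7.1.1) carries the endpoint as "AEs leading to discontinuation of study drug", with one tick, read under 3&FU (ivS). The prostacyclin-associated row that also ends "leading to discontinuation of study drug" has one tick, under Period 2.

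The SAP rules that give the tick its meaning are:

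- Section 5.5: i.v. selexipag is the only study treatment.
- Section 7.2.1.4: "An AE is considered as leading to discontinuation of study treatment if the investigator ticked" the option 'Drug withdrawn'.
- Section 7.2.2: "The start date/time of the AE record from the CRF will be used to assign the AE to a study period". The same section ties the AE summary tables to the periods in Table 7.
- Section 10.2.1: "The end date and time of the last infusion of i.v. selexipag will be considered study treatment end date/time".
- Section 2.3, Table 2: Period 3 starts with the oral evening dose on Day 3.

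SAP 11.1 declares no changes to the protocol's analyses, and 11.3 does not mention this row.

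**The concern.** The primary objective is the tolerability of the switch, so the proportion of subjects who stop i.v. drug because of any AE is a natural headline figure. The all-cause row matters because the prostacyclin list in SAP 7.2.1.6 (headache, diarrhea, nausea and similar terms) contains neither hypotension nor right heart failure, while protocol 5.1.11 gives symptomatic hypotension and new signs of right heart failure as reasons for stopping i.v. treatment. A stop for either would be absent from the prostacyclin row and should be counted in the all-cause row.

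As read, the all-cause row looks only at AEs that start after i.v. treatment has ended. It also sits in a different period from its own subset, so the prostacyclin-associated row could show 1/18 while the all-cause row shows 0/18.

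**Working it through.** **1. Position of the tick.** Splitting Table 7 on its cell separators gives 8 cells in the header and 8 in each row checked. The prostacyclin discontinuation and injection site rows fall under Period 2. The all-cause discontinuation row falls under 3&FU. The next row (related AEs) falls under 2, 3&FU, 2&3&FU and 1&2&3&FU.

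**2. What that column can contain.** The last infusion is on the morning of Day 3 (protocol Tables 2 and 3), and Period 3 starts that evening. Protocol 5.1.10 defines premature discontinuation as the third infusion not being started, which is settled within Period 2. An AE starting in Period 3 or follow-up cannot have caused it. Imputation does not change this: a fully missing AE start becomes "Date & time of first i.v. selexipag" (SAP 10.5), which is the start of Period 2. Apart from recording errors, the count under 3&FU is zero.

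**3. The plan's own precision figures.** SAP 2.5 gives upper limits of 35% (n = 18) and 32% (n = 20). The exact (Clopper-Pearson) limits for x events in n are:

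- lower = Beta quantile(0.025; x, n − x + 1)
- upper = Beta quantile(0.975; x + 1, n − x)

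With x = 2:

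- 2/18 = 11.1%, interval 1.4% to 34.7%
- 2/20 = 10.0%, interval 1.2% to 31.7%

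Both upper limits match the stated figures.

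**4. Real result against tabulated result, n = 18.** For x = 0 the upper limit is 1 − 0.025^(1/18) = 18.5%.

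| Real i.v. stops in Period 2 | True display | Display under 3&FU |
|---|---|---|
| 1 | 5.6% (0.1% to 27.3%) | 0% (0% to 18.5%) |
| 2 | 11.1% (1.4% to 34.7%) | 0% (0% to 18.5%) |

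**5. How likely a real stop is.** The documents give no any-AE rate. As an assumption, take their 5% to 10% range for prostacyclin-associated discontinuation. P(at least one stop among 18) = 1 − (1 − p)^18, which is 60% at p = 5%, 75% at 7.5% and 85% at 10%. The 7.5% came from titration and maintenance in the earlier pivotal study, so the rate over 36 hours at a stable dose may be lower.

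**6. If the printed tick is under Period 2.** Comparing with protocol 6.2.3:

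- 1&2 is missing. An AE that began in Period 1 and led to i.v. withdrawal is assigned to Period 1 by its start time and is not counted in this row.
- 2&3 is missing, although by step 2 its count would equal that of Period 2.
- Period 1 alone and 3&FU alone are missing.
- The overall span in protocol 10.3.4 is missing.

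**The case against.** **The tick may be displaced.** The reading depends on one mark in a table taken from a PDF, and equal cell counts do not exclude a shift. In the same text, the T_EXP_IV layout in SAP Appendix E shows the 1575 and 1800 µg rows under the 200-1000 µg group, one column off. Period 2 is also the sensible place for the mark. This stands, so the structural zero can only be stated conditionally. Step 6 holds in either case.

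**Other outputs show i.v. stops.** A reader might infer that i.v. stops disappear from the report. The documents do not support that:

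- The PWDT table and listing give all premature i.v. discontinuations by reason.
- T_EXP_ADJ shows premature discontinuation at each infusion.
- AE_DC_RMP covers risk-plan categories, including hypotension.
- The AE_DC listing has no period limit.
- Prostacyclin-associated stops are planned for Period 2.

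This also stands. These outputs do not replace the summary, however: the PWDT layout has no AE category of its own and no confidence interval.

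**AE_DC_PT may cover the whole study.** Its title (SAP 12.7.7) lacks the by-period wording of AE_REL_PT and AE_PAH_PT, so a programmer could run it over all periods. But SAP 7.2.2 ties it to Table 7, and its layout, T_AE_PT, carries period labels. The instruction is ambiguous, so a zero is not certain even with the tick as read.

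**Stopping reasons.** A reader might add infusion reactions to the stops at risk of being missed. Protocol 5.1.11 does not name them, and the point does not rely on them.

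**Conclusion.** The point holds in limited form. The all-cause discontinuation row has a single period, which is narrower than protocol 6.2.3 and is not declared in SAP 11.1.

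If the printed tick is under 3&FU and the table is run as SAP 7.2.2 directs, the summary is 0/18 (0% to 18.5%) for any outcome of the infusions, where two real stops would give 11.1% (1.4% to 34.7%). If the printed tick is under Period 2, the zero disappears. What remains is the missing combined periods and the uncounted withdrawals from AEs that began in Period 1.

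The stronger readings, that the endpoint is certainly zero or that i.v. stops are planned nowhere, go beyond the documents. The damage is to one period summary of a descriptive endpoint, with no loss of data. The figures assume 18 subjects in the i.v. Safety Set, as planned.

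**What to change.** 1. Check the printed position of the tick in Table 7.
2. For this row, tick Period 2, 1&2, 2&3&FU and 1&2&3&FU. Tick Period 1 and 3&FU as well, as protocol 6.2.3 lists them, or declare their omission in SAP 11.1.
3. State the periods in the title of AE_DC_PT, and say that the 1&2&3&FU column counts every AE marked 'Drug withdrawn'. The start-time rule already gives this, except for an AE that began in screening, so say explicitly that such an AE is counted.
4. AE_DC_PT is listed for the i.v. Safety Set only. The 1&2 and 1&2&3&FU columns in Table 7 use the Safety Set, as protocol 10.3.4 asks, so add that set where the two differ.

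The cost is one table row, one output title and one analysis-set entry. No new data or layout is needed.
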